5.1 Agent Administration

Reported adverse events and potential risks are described in [Section 7](#). Appropriate dose modifications are described in [Section 6](#). No investigational or commercial agents or therapies other than those described below may be administered with the intent to treat the patient's malignancy.

TRC102 will be administered to patients as a capsule dosed according to the dose escalation table. TRC102 should be administered together with TMZ capsules. TRC102/TMZ should be administered either 1 hour before or 2 hours after a meal. Patients should drink an eight ounce glass of water following TRC102/TMZ administration. Antiemetic therapy may be administered prior to and/or following administration of TRC102/TMZ in patients who develop nausea and vomiting but not prophylactically. TRC102/TMZ capsules should not be opened or chewed. If capsules are accidentally opened or damaged, precautions should be taken to avoid inhalation or contact with the skin or mucous membranes.

The drugs will be administered in 28-day cycles (\pm 1 day for scheduling). A missed or vomited dose will not be replaced. The patients will be instructed to take the next scheduled dose at the regularly scheduled time. Patients will be asked to maintain a Study Medication Diary ([Appendix C](#)) and record each dose of medication. Patients will be given instructions for completing the medication diary and will be asked to return it to the clinic staff at the end of each cycle.

5.2 Definition of Dose-Limiting Toxicity (Phase I only)

For MTD determination, DLTs will be defined as toxicities occurring within the first cycle of treatment. Patients who come off study for reasons other than drug-related toxicity (e.g., disease progression) prior to completion of more than 90% of dose of the first cycle will be replaced. Dose-limiting toxicity (DLT) is defined as an adverse event that occurs during the first cycle and is felt to be related (possibly, probably, or definitely) to administration of study drugs and fulfills one of the following criteria:

5.2.1 Hematologic Toxicity

- 5.2.1.1 Grade 4 neutropenia
- 5.2.1.2 Febrile neutropenia
- 5.2.1.3 Neutropenic infection: Grade ≥ 3 neutropenia with grade ≥ 3 infection.
- 5.2.1.4 Grade ≥ 3 thrombocytopenia
- 5.2.1.5 A drop in Hgb ≥ 3.0 g/dL over one week
- 5.2.1.6 Any degree of lymphopenia, or leukopenia in the absence of grade 4 neutropenia will not be considered dose limiting.

- 5.2.2 Grade ≥ 3 Non-hematologic Toxicity
 - 5.2.2.1 Grade ≥ 3 non-hematological toxicity (except alopecia) felt to be related to study medications will be considered dose-limiting with the following clarifications:
 - 5.2.2.2 Diarrhea Grade 3 will only be considered dose-limiting if it is refractory to treatment as outlined in [Section 5.3.2](#), Supportive Care Guidelines, and unable to be corrected to Grade 2 or less within 24 hours. Bloody or Grade 4 diarrhea will be dose-limiting.
 - 5.2.2.3 Nausea and vomiting Grade 3 will only be considered dose-limiting if it is refractory to anti-emetic therapy and unable to be corrected to Grade 1 or less within 24 hours ([Section 5.3.1](#)).
 - 5.2.2.4 Rise in creatinine to Grade 3, not corrected to Grade 1 or less within 48 hours with IV fluids will be considered dose-limiting. All Grade 4 rises in creatinine will be dose limiting.
 - 5.2.2.5 Grade ≥ 3 electrolyte abnormalities will not be considered dose limiting. Grade 4 metabolic toxicities that are symptomatic will be considered dose-limiting regardless of duration or ability to correct.

Management and dose modifications associated with the above adverse events are outlined in [Section 6](#). Dose escalation will proceed within each cohort according to the following scheme.

Number of Patients with DLT at a Given Dose Level	Escalation Decision Rule
0 out of 3	Enter 3 patients at the next dose level.
≥ 2	Dose escalation will be stopped. This dose level will be declared the maximally administered dose (highest dose administered). Three (3) additional patients will be entered at the next lowest dose level if only 3 patients were treated previously at that dose.
1 out of 3	Enter at least 3 more patients at this dose level. 
 • If 0 of these 3 patients experience DLT, proceed to the next dose level. • If 1 or more of this group suffer DLT, then dose escalation is stopped, and this dose is declared the maximally administered dose. Three (3) additional patients will be entered at the next lowest dose level if only 3 patients were treated previously at that dose.
≤ 1 out of 6 at highest dose level below the maximally administered dose	This is generally the recommended phase 2 dose. At least 6 patients must be entered at the recommended phase 2 dose.

5.3 General Concomitant Medication and Supportive Care Guidelines

All patients will be provided with the best available supportive care. All concurrent medications should be documented prior to initiation of treatment, and be periodically reviewed with the patient. Particular attention must be paid to medications which may cause hemolytic anemia.

No other approved or investigational anticancer treatment will be permitted during the study period, including chemotherapy, biologic response modifiers, hormone therapy, immunotherapy, or radiotherapy.

5.3.1 Nausea/Vomiting

Anti-emetics will not be administered routinely prior to TMZ or TRC102. However, if a patient develops nausea/vomiting, anti-emetics such as but not limited to prochlorperazine, metoclopramide, 5-HT3 antagonists, or aprepitant may be given. In addition, if a patient develops nausea and/or vomiting that is Grade 2 or greater, anti-emetics may be instituted prophylactically at the discretion of the investigator. Nausea and vomiting will be considered refractory if it does not resolve to \leq Grade 1 with treatment with a combination of at least 2 of the antiemetics within 24 hours.

5.3.2 Diarrhea

If diarrhea develops and does not have an identifiable cause other than study drug administration, anti-diarrheals such as Lomotil (diphenoxylate HCl 2.5 mg + atropine sulfate 0.025 mg/tablet) dosed according to package insert or loperamide 4 mg po after

the first unformed stool with 2 mg po every 2 hours as long as unformed stools continue (4 mg every 4 hours while asleep). No more than 16 mg of loperamide should be taken in during a 24-hour period. This regimen can be repeated for each diarrheal episode.

Diarrhea will be considered refractory if it does not resolve within 24 hours \leq to Grade 2 with the above regimen (16 mg, or less if there is resolution of the symptoms, of loperamide in a 24-hour period).

5.3.3 *Neutropenia*

Febrile neutropenia is a life-threatening complication requiring hospitalization and urgent broad-spectrum antibiotics, as well as an aggressive search for the source and microbial cause of the episode. Growth factors to prevent neutropenia will not be administered prophylactically. If necessary, they may be administered according to accepted American Society of Clinical Oncology (ASCO) guidelines to allow re-treatment.

5.3.4 *Anemia*

Symptomatic anemia should be treated with red blood cell transfusion and is recommended if the hemoglobin falls below 8 g/dL. Use of erythropoietin will follow ASCO guidelines.

5.3.5 *Thrombocytopenia*

Thrombocytopenia will be treated conservatively. In the absence of bleeding, or a necessary invasive procedure, platelet transfusions should be given for a platelet count \leq 10,000/mm³. If invasive procedure(s) is (are) planned, or the patient develops bleeding, platelet transfusions should be administered in accordance with the standard of practice, usually maintaining a platelet count above 50,000/mm³.

5.4 Duration of Therapy

In the absence of treatment delays due to adverse event(s), treatment may continue until one of the following criteria applies:

- Disease progression
- Intercurrent illness that prevents further administration of treatment
- Significant toxicity occurs despite 2 dose reductions as described in [Section 6](#) or no lower dose level exists
- Pregnancy
- Patient decides to withdraw from the study
- General or specific changes in the patient's condition render the patient unacceptable for further treatment in the judgment of the investigator.

5.5 Duration of Follow Up

Patients will be followed for 30 days after the last dose is administered or until one of the following occurs: patient enrolls on another protocol, patient receives standard of care, or death, whichever comes first. The follow-up will consist of a phone call between Days 27-30 after the last dose to evaluate adverse events that were ongoing and any new events that might be deemed related to the therapy. Toxicities felt to be possibly, probably, or definitely related to the study drugs that have not resolved or stabilized by Day 30 post-treatment will be followed until stabilization or resolution via phone calls as clinically indicated. Whenever possible, Phase II patients will be followed via phone calls until they progress or start another treatment for their cancer.

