- 3.1.9 Patients must have completed any chemotherapy, radiation therapy, or biologic therapy \geq 4 weeks (or 5 half-lives, whichever is shorter) prior to entering the study (6 weeks for nitrosoureas or mitomycin C). Patients must be \geq 2 weeks since any prior administration of a study drug in a Phase 0 or equivalent study and \geq 1 week from palliative radiation therapy. Patients must have recovered to eligibility levels from prior toxicity or adverse events. Treatment with bisphosphonates is permitted.
- 3.1.10 Patients must be able to swallow whole tablets or capsules; nasogastric or G-tube administration is not allowed.
- 3.1.11 Ability to understand and the willingness to sign a written informed consent document and to undergo tumor biopsies in the expansion phase.

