5.6 Criteria for Removal from Study

Patients will be removed from study for one of the following reasons: completed 30-day follow-up period or toxicities are unresolved but stabilized. The reason for study removal and the date the patient was removed must be documented in the medical record and communicated to Central Registration per [Section 4](#).

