7.2.3.2 Expedited Reporting Guidelines

Use the NCI protocol number and the protocol-specific patient ID assigned during trial registration on all reports.

Note: A death on study requires both routine and expedited reporting regardless of causality, unless as noted below. Attribution to treatment or other cause must be provided.

Death due to progressive disease should be reported as **Grade 5 “Disease Progression”** in the system organ class (SOC) ”General disorders and administration site conditions.” Evidence that the death was a manifestation of underlying disease (e.g., radiological changes suggesting tumor growth or progression; clinical deterioration associated with a disease process) should be submitted.

Expedited Reporting Requirements for Adverse Events that Occur on Studies under an IND/IDE within 30 Days of the Last Administration of the Investigational Agent/Intervention ^{1,2}

FDA REPORTING REQUIREMENTS FOR SERIOUS ADVERSE EVENTS (21 CFR Part 312)

NOTE: Investigators **MUST** immediately report to the sponsor (NCI) **ANY** Serious Adverse Events, whether or not they are considered related to the investigational agent(s)/intervention (21 CFR 312.64)

An adverse event is considered serious if it results in **ANY** of the following outcomes:

- 1) Death
- 2) A life-threatening adverse event
- 3) An adverse event that results in inpatient hospitalization or prolongation of existing hospitalization for \geq 24 hours
- 4) A persistent or significant incapacity or substantial disruption of the ability to conduct normal life functions
- 5) A congenital anomaly/birth defect.
- 6) Important Medical Events (IME) that may not result in death, be life threatening, or require hospitalization may be considered serious when, based upon medical judgment, they may jeopardize the patient or subject and may require medical or surgical intervention to prevent one of the outcomes listed in this definition. (FDA, 21 CFR 312.32; ICH E2A and ICH E6).

ALL SERIOUS adverse events that meet the above criteria **MUST** be immediately reported to the NCI via CTEP-AERS within the timeframes detailed in the table below.

Hospitalization	Grade 1 and Grade 2 Timeframes	Grade 3-5 Timeframes
Resulting in Hospitalization \geq 24 hrs	10 Calendar Days	24-Hour 5 Calendar Days
Not resulting in Hospitalization \geq 24 hrs	Not required	

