7.3.4 NCI Clinical Director Reporting

Problems expeditiously reported to the OHSRP/IRB in iRIS will also be reported to the NCI Clinical Director. A separate submission is not necessary as reports in iRIS will be available to the Clinical Director.

In addition to those reports, all deaths that occur within 30 days after receiving a research intervention should be reported via email to the Clinical Director unless they are due to progressive disease.

To report these deaths, please send an email describing the circumstances of the death to the Clinical Director/designee at [contact] within one business day of learning of the death.

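### Section 5.5 lets planned follow-up end when a patient starts other treatment, while Sections 5.6, 7.2.3.2 and 7.3.4 rest on a full 30 days after the last dose

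*Combined protocol and SAP*

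**What the plan says.** Section 5.5 sets the nominal period and its exits in one sentence: "Patients will be followed for 30 days after the last dose is administered or until one of the following occurs", the exits being "patient enrolls on another protocol, patient receives standard of care, or death, whichever comes first". It then gives the one contact that has a date: "The follow-up will consist of a phone call between Days 27-30 after the last dose". A separate sentence covers related toxicities "that have not resolved or stabilized by Day 30 post-treatment will be followed until stabilization or resolution", and it states no exception for new treatment. Phase II patients are also phoned where possible, but those calls stop at progression or at the start of another cancer treatment.

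Section 5.6 gives the reasons for removal from study as "completed 30-day follow-up period or toxicities are unresolved but stabilized". Starting other therapy is not among them.

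The main table in Section 7.2.3.2 is headed "Expedited Reporting Requirements for Adverse Events that Occur on Studies under an IND/IDE within 30 Days of the Last Administration of the Investigational Agent/Intervention", and the section requires serious events to be reported irrespective of attribution. Section 7.3.4 says that "all deaths that occur within 30 days after receiving a research intervention should be reported" to the Clinical Director, except those due to progressive disease. Neither section shortens the window when new therapy begins.

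The study calendar in Section 10 has an off-treatment column that includes an adverse event evaluation. Its footnote calls this an off-study evaluation and gives no day.

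**The concern.** Safety and tolerability are a primary objective (Section 1.1), and the reporting rules assume that the site knows what happened to each patient for 30 days. Under Section 5.5 as written, a patient who switches on day 24 is outside follow-up on day 28, and nobody is required to make the call. Section 5.6 suggests that the same patient is still on study. A site cannot tell which applies.

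Late events are plausible on the protocol's own account. Sections 2.3 and 7.1.1 warn of liver toxicity after temozolomide has been stopped, and Section 2.5 reports hemolytic anemia as the dose-limiting toxicity. From cycle 2, Section 5 schedules laboratory tests only before each cycle, so events in the weeks after the last dose come to light largely through follow-up contact. Patients who move quickly to other treatment are unlikely to be a random subset, so safety information would be thinner for a particular kind of patient.

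**Working it through.** The plan states no figure on this point, so there is none to reproduce. The check compares the sections and then does the window arithmetic.

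**Comparison of the sections**

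| Section | Period | Ends at new therapy? |
|---|---|---|
| 5.5, general follow-up and call | 30 days | Yes |
| 5.5, related unresolved toxicity | To stabilization or resolution | Not stated |
| 5.6, removal from study | 30-day period completed, or toxicities stabilized | Not listed |
| 7.2.3.2, serious events | 30 days | No |
| 7.3.4, deaths | 30 days | No |

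The standard-of-care exit in Section 5.5 is not limited to anticancer treatment, so a literal reading could end follow-up earlier still.

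**Days lost**

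Let x be the days from last dose to the start of other therapy. Days outside follow-up = max(0, 30 − x). The call is not required if x < 27.

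| x | Days lost | Call falls after follow-up ends? |
|---|---|---|
| 7 | 23 | Yes |
| 14 | 16 | Yes |
| 21 | 9 | Yes |
| 23 | 7 | Yes |
| 26 | 4 | Yes |
| 28 | 2 | Not necessarily |
| 30 | 0 | No |

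**Which x is typical**

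Dosing is on days 1-5 of a 28-day cycle and restaging is every 2 cycles (Section 10). If the scan is taken at the end of cycle k, that is day 28k, and the last dose was on day 28(k − 1) + 5. The difference is 28 − 5 = 23 days. A patient who progresses at that scan and switches at once loses 30 − 23 = 7 days and the call. The exact scan day is not fixed, so the loss can be somewhat larger or smaller.

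**Upper range**

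Assume that the next treatment is a trial with the washout in Section 3.1.9, "4 weeks (or 5 half-lives, whichever is shorter) prior to entering the study". Section 2.2 gives TRC102 half-lives of 28 h (oral, with pemetrexed) and 55.04 h (one-hour infusion).
- 5 × 28 h = 140 h = 5.8 days, which leaves 30 − 5.8 = 24.2 days.
- 5 × 55.04 h = 275.2 h = 11.5 days, which leaves 30 − 11.5 = 18.5 days.
- A 4-week washout instead leaves 30 − 28 = 2 days.

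**How many patients**

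The documents give no share of patients who switch within 30 days. As an illustration on the Phase II ceiling of 75: 10% is 7.5, 25% is 18.75 and 50% is 37.5, or about 8, 19 or 38 patients.

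**The case against.** The strongest reply is that a site can comply with both sections. Section 7 applies whenever an event becomes known, whatever Section 5.5 says. It also requires reports of related serious events after day 30, when no routine contact exists, so a reporting window longer than active follow-up is not in itself an error. Stopping collection at new therapy can also be a deliberate choice, to avoid events that are hard to attribute. And the completed 30-day period in Section 5.6 might be meant as the follow-up that Section 5.5 defines, exits included.

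Much of this stands. It shows that the reporting duty survives. It does not show that the events will be found, and the intended reading of Section 5.6 is not stated.

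A reader might also infer more than the documents support:
- **That follow-up of unresolved related toxicity stops at the switch.** That sentence in Section 5.5 has no such exit, and Section 6 separately requires patients stopped for unresolved toxicity to be followed.
- **That the call is the only planned safety contact.** The calendar has an off-treatment evaluation. Without a day it does not secure the 30 days, but it exists.
- **That sites are told to close the patient on the first day of new therapy.** Section 5.6 does not say so.
- **That 18 to 24 days are usually lost.** That needs an exit well before the scheduled scan, an outside trial that borrows this protocol's washout, and half-lives from other regimens.
- **That the Phase I dose finding is compromised.** Section 5 requires a DLT or a full cycle of follow-up for evaluability, which largely protects it.

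**Conclusion.** The inconsistency is real and should be corrected. Section 5.5 ends planned follow-up at new treatment, and Sections 5.6, 7.2.3.2 and 7.3.4 contain no matching exit. What is lost is active ascertainment of new adverse events, unrelated serious events and deaths between the switch and day 30. The days before the switch are observed.

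For progression at a scheduled end-of-cycle scan with an immediate switch, the loss is about 7 of 30 days plus the call. This assumes that the scan falls at the end of the 28-day cycle. Patients who leave earlier for toxicity, withdrawal or clinical progression can lose more, and those who switch on day 30 or later lose nothing. The number affected is unknown.

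A reader might infer a demonstrated downward bias in the trial's safety results. The documents do not support that: they give no switching rate, and Section 13 plans no analysis of post-treatment events or 30-day mortality. Under-ascertainment would tend to lower such counts, but its size cannot be estimated. No sample size or error rate is affected.

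**What to change.** Amend Section 5.5 so that it agrees with Sections 5.6, 7.2.3.2 and 7.3.4. Suggested wording: *Adverse events (at a minimum, serious adverse events) and vital status will be ascertained for all patients through 30 days after the last dose of TRC102/TMZ, including the day 27-30 telephone contact, regardless of enrollment on another protocol or start of other treatment, except after death or withdrawal of consent. The start date of any new therapy will be recorded.* It would also help to say, in the calendar footnote, how the off-treatment evaluation relates to this period.

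The cost is one amended sentence, a call that is already planned but would now be made to every patient, and one extra date to collect. The downside is that events after the switch are harder to attribute. The recorded start date lets them be reported separately, which limits this.

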5. TREATMENT PLAN

Phase I: This is an open-label Phase I trial evaluating the combination of oral TRC102 with oral TMZ, in 28-day cycles. The starting dose of TRC102 is based on the safety information from the trial of IV TRC102 combined with TMZ. The study will follow a 3+3 design: dose will be escalated in cohorts of 3 patients with the individual dose of TRC102 and TMZ increased in successive dose levels as outlined in the dose escalation table below. Once the MTD is established, up to 15 additional patients will be enrolled at the MTD (expansion phase) to further define the dose and evaluate PK and PD at this dose level.

Phase II: Patients with a body surface area (BSA) of $\geq 1.6 \text{ m}^2$ will be started on 125 mg TRC 102 and 150 mg/m² Temozolomide orally on days 1-5 of each 28-day cycle (DL6). Patients with a BSA of $< 1.6 \text{ m}^2$ will be started on 100 mg TRC 102 and 150 mg/m² Temozolomide orally on days 1-5 of each 28-day cycle (DL5). There will be no dose escalation for patients on the Phase II portion of the study; appropriate dose modifications are described in [Section 6](#). Up to 75 patients will be accrued to this part of the study.

History and physical examination can be done up to 8 days before start of a new cycle. Patients will be examined at baseline for the first cycle then at the start of every cycle for the remainder of the study (up to 3 days before start of a new cycle). The start of the next cycle may be delayed for up to 1 week to accommodate scheduling conflicts.

Labs (CBC with differential; serum chemistries) will be performed (+/- 2 days) as follows: every week up to week 3 for cycle 1. Starting with cycle 2, labs (CBC with differential; serum chemistries) will only be performed before the start of each cycle (laboratory evaluation may be performed up to 7 days prior to scheduled date to accommodate scheduling conflicts and patient convenience). If clinically indicated, labs may be obtained more frequently.

Blood for erythrocyte analysis (optional) will be collected on cycle 1 days 7, 14, and 21 (+/- 2 days) as described in [Appendix F](#).

CT scans will be performed at baseline, and repeat scans will be performed every 2 cycles (every 3 cycles for patients on study more than one year).

Phase I Dose Escalation Schedule (28-day cycle)		
Dose Level	TRC 102 orally	TMZ orally
Level -2	25 mg once daily D1-5	75 mg/m ² once daily D1-5
Level -1	25 mg once daily D1-5	100 mg/m ² once daily D1-5

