10. STUDY CALENDAR

Baseline evaluations are to be conducted within 8 days prior to start of protocol therapy. Scans and x-rays must be done \leq 4 weeks prior to the start of therapy. In the event that the patient's condition is deteriorating, laboratory evaluations should be repeated within 48 hours prior to initiation of the next cycle of therapy. Start of next cycle may be delayed for up to 1 week to accommodate scheduling conflicts. History and physical examination and laboratory evaluations can be performed up to 1 week before the start of the next cycle.

	Pre-Study	C1 W1	C1 W2 ^k	C1 W3 ^k	C1 W4 ^k	C2 W1 ^k	C2 W3	C3 W1 ^k	C3 W3 ^k on	Off Treatment ^j
TRC102/TMZ ^a		X				X		X		
Informed consent	X									
Demographics	X									
Medical history	X					X		X		
Concurrent meds	X	X-----						X		
Physical exam ^b	X	X				X		X		X

Vital signs	X					X		X		X
Height	X									
Weight	X					X		X		X
Performance status	X					X		X		X
CBC w/diff, plts ^c	X		X	X		X		X		
Serum chemistry ^c	X		X	X		X		X		
Anemia ^l	X	X	X							
PT, INR, PTT ^d	X									
β-HCG ^e	X									
AE evaluation			X-----X							X
Tumor measurements	X		Tumor measurements are repeated every 2 cycles (3 cycles for patients on study more than 1 year). Documentation (radiologic) must be provided for patients removed from study for progressive disease.							
Tumor biopsy ^f	X	X								
PK blood ^g		X								
Circulating tumor cells ^h		X				X				X
ECG ⁱ	X									

a: TRC102 and TMZ will be administered once daily, days 1-5, in 28 day cycles.
b: Physical exam at the Clinical Center should be performed at the start of each cycle (up to 1 week before start of a new cycle). Start of the next cycle may be delayed for up to 1 week to accommodate scheduling conflicts.
c: Serum chemistry (albumin, total bilirubin, calcium, creatinine, phosphorus, magnesium, potassium, sodium, SGOT [AST], SGPT [ALT], LDH); CBC w/diff, platelets up to week 3 during cycle 1 (Phase I only), and during week 1 in cycle 2 and subsequent cycles (up to 1 week before start of a new cycle) (Phase I and II). If clinically indicated, labs may be obtained more frequently.
d. PT/INR, PTT as clinically indicated.
e: Serum pregnancy test (women of childbearing potential) within 8 days prior to enrollment and as clinically indicated.

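### No CBC or chemistry panel is required after the final doses when a patient's last cycle is cycle 2 or later

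*Combined protocol and SAP*

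**What the plan says.** Section 5 (Treatment Plan) sets cycle 1 laboratory tests at "every week up to week 3 for cycle 1". After that, "Starting with cycle 2, labs (CBC with differential; serum chemistries) will only be performed before the start of each cycle", and the "laboratory evaluation may be performed up to 7 days prior to scheduled date". Extra tests are discretionary: "If clinically indicated, labs may be obtained more frequently".

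Footnote c of the Section 10 calendar agrees for later cycles, in both phases: "during week 1 in cycle 2 and subsequent cycles (up to 1 week before start of a new cycle". For cycle 1 it differs from Section 5, because it restricts the weekly tests by phase: "CBC w/diff, platelets up to week 3 during cycle 1 (Phase I only".

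In the calendar, the CBC and serum chemistry rows are marked at pre-study, cycle 1 weeks 2 and 3, and week 1 of cycles 2 and 3. Both are blank in the Off Treatment column. That column is marked for physical exam, vital signs, weight, performance status, AE evaluation and circulating tumor cells. Footnote j labels the column as the off-study evaluation and says nothing more.

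Section 5.5 describes follow-up after the last dose as "a phone call between Days 27-30 after the last dose to evaluate adverse events that were ongoing and any new events" that might be related to treatment. Related toxicities still open at day 30 are followed by telephone.

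**The concern.** From cycle 2, each panel precedes its own cycle's doses and in effect checks the cycle before. The last cycle is checked only if another is about to start. Even the repeat tests that Section 10 asks for when a patient is deteriorating are tied to starting the next cycle.

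This matters because the expected toxicity is largely seen in the laboratory. Section 2.5 reports hemolytic anemia as the dose-limiting toxicity, with the MTD exceeded at dose level 8. The TRC102 risk list in Section 7.1 includes anemia and increased blood bilirubin. For temozolomide, Section 7.1.1 lists thrombocytopenia and neutropenia among the common grade 3-4 abnormalities and calls for neutrophil and platelet monitoring throughout treatment. Safety and tolerability are a primary objective (Section 1.1), and Section 11.1.1 makes every treated patient evaluable for toxicity from the first dose. A laboratory abnormality that produces no symptoms after the final doses could be missing from that record.

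**Working it through.** There is no stated figure to reproduce. The check sets the schedule against the dosing days and counts.

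**Inputs.** Doses on days 1-5 of a 28-day cycle (Section 10, footnote a). Pre-cycle panel 0 to 7 days before day 1, from cycle 2 (Section 5; footnote c). Call on days 27-30 after the last dose (Section 5.5). Phase II accrual ceiling of 75 (Section 13.2).

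**Required panels after a cycle's doses**

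| Cycle | Required post-dose panels |
|---|---|
| Cycle 1, following Section 5 | 2 (calendar weeks 2 and 3) |
| Cycle 2 or later, followed by another cycle | 1 (the next cycle's pre-cycle panel) |
| Cycle 2 or later, final | 0 |
| Phase II, stopping after cycle 1 | 2 if Section 5 governs; 0 if footnote c governs |

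Phase I patients who stop after cycle 1 are not affected, because their week 2 and week 3 panels follow the doses.

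**Length of the gap when no panel was drawn for the cancelled cycle**

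- Last required draw: day 1 minus 0 to 7 days, which is cycle day 1 to cycle day -6.
- Day 30 after the last dose: 5 + 30 = cycle day 35.
- Interval to day 30: 35 - 1 = 34 days, up to 35 - (-6) = 41 days.
- Measured to the call instead: the call falls on cycle days 5 + 27 = 32 to 5 + 30 = 35, so the interval is 32 - 1 = 31 to 35 - (-6) = 41 days.

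Visit windows move these by a day or two. Follow-up can also end sooner, on another protocol, standard of care or death.

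**Patients without a required panel (illustration).** Let f be the share of Phase II patients in scope and q the share of their final cycles with no panel drawn for a cancelled next cycle. The documents give neither. If footnote c governs, f = 1. If Section 5 governs, f is below 1, and 0.7 is used here as an assumption. The count is N x f x q. N = 75 is the ceiling. N = 40 is the evaluable total if all three cohorts stop at stage one (16 + 16 + 8, Section 13.1).

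| Assumed q | 75, f = 1 | 75, f = 0.7 | 40, f = 1 | 40, f = 0.7 |
|---|---|---|---|---|
| 0 | 0 | 0 | 0 | 0 |
| 0.1 | 7.5 | 5.25 | 4 | 2.8 |
| 0.25 | 18.75 | 13.1 | 10 | 7 |
| 0.5 | 37.5 | 26.25 | 20 | 14 |

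These count patients without a required panel, not missed events. Phase I patients whose last cycle is cycle 2 or later are also in scope but are not included.

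**The case against.** The strongest reply is that little turns on this. DLTs are confined to cycle 1, and Section 13 contains no analysis, rate or stopping rule based on later-cycle laboratory values. That is correct: the effect is on safety monitoring and reporting only.

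The second reply is that most routes off treatment already bring a panel or follow-up. Because "repeat scans will be performed every 2 cycles", stops for progression tend to fall near a cycle boundary, where a pre-cycle panel may already exist; such a patient has no gap. Section 6 follows patients stopped for unresolved toxicity. Symptomatic patients are seen at the off-treatment exam and AE evaluation and can have clinically indicated tests. This argues for the low end of the table, and the higher values of q should be read in that light. It does not close the gap, because these safeguards need a symptom, an abnormality already found, or a draw that happened to be made. The liver monitoring in Section 6 names no post-treatment draw.

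Third, the risk is moderated. Phase II uses dose levels 5 and 6, below the level where the MTD was exceeded. Section 2.5 reports no cumulative hematologic toxicity in preclinical work, and transfusions in the first three cycles are reported under Section 7.2.4. Severe late anemia is therefore less likely. Lesser falls, low counts and liver test changes remain possible.

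Finally, one panel has limits. The Off Treatment visit has no stated timing, so the draw may miss a nadir. Haptoglobin, also on the risk list, is outside the routine chemistry panel. Patients who withdraw may not attend. All of this stands, and it bounds what the change can deliver.

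**Conclusion.** The gap is real and follows from the text: zero required CBC or chemistry panels after the doses of a final cycle numbered 2 or later, against one for earlier cycles from cycle 2. Where no pre-cycle panel was drawn for the cancelled cycle, 34 to 41 days pass to day 30 after the last dose without a required test. The same may hold for Phase II patients who stop after cycle 1, depending on whether Section 5 or footnote c governs.

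The consequence is confined to asymptomatic or laboratory-only toxicity. How many patients are affected cannot be known from the documents; the counts rest on assumed q and, if Section 5 governs, assumed f, and they start at zero. This is a modest weakness in safety capture that should be corrected because the remedy is cheap.

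**What to change.** In the Section 10 calendar, mark the CBC and serum chemistry rows in the Off Treatment column. Accept in place of a new draw any panel taken after the last doses and within 7 days before that visit.

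For patients who attend, this raises required post-dose panels in the final cycle from 0 to 1, matching the other cycles from cycle 2. It also covers Phase II patients who stop after cycle 1, whichever of Section 5 and footnote c governs.

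The cost is two calendar cells and at most one routine draw at an existing visit, or none where a qualifying panel exists. Sample size and error rates do not change. Section 2.3 notes that temozolomide liver injury can appear several weeks after treatment stops, so the added panel narrows that risk without removing it.
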